## 8.2 Use of Electronic Medical Record

The electronic medical record (Epic) will be used to extract the following social and medical history. Demographic data (e.g., age, date of birth, gender, race/ethnicity, and insurance type) will be obtained from the patient’s electronic medical record, and verified via self-report. Demographic variables will likely be used as covariates in analyses. Results of physical examinations, particularly urological and gynecological history as well as urinary symptoms, will be used to determine inclusion criteria. History and diagnoses of serious illness that would preclude study participation will be extracted to determine exclusion criteria (see section 3.2 above). In addition, substance and alcohol use history and diagnoses will be accessed through Epic to establish the exclusion criterion of substance use disorder. Lastly, mental health history and diagnoses will be pulled from Epic for inclusion/exclusion criteria, and to provide background information for therapists.

### 8.3 Measures

Participants will be asked to complete questionnaires at baseline, mid-treatment (after 6 sessions), posttreatment (after 12 sessions), at a 3-month follow-up, and at a 6-month follow-up. Baseline, mid-treatment, and posttreatment assessments will be completed on tablets with a link from REDcap, though participants will have the option to

respond on paper forms. Both follow-up assessments will be carried out online with a link sent via email. The primary outcome tool for this study will be the six-item Urinary Distress Inventory (UDI-6), which is a subscale of the Pelvic Floor Distress Inventory (PFDI), as measure of urinary symptoms. We will also measure anxiety using a short form from the NIH Patient Reported Outcomes Measurement Information System (PROMIS), which has been shown to be reliable and valid; this form is brief and easy to complete. Secondary measures include the PROMIS profile (depression, fatigue, pain, physical function, sleep disturbance, and social roles), trauma history assessed with the PTSD Checklist for DSM-5 with Life Events Checklist (PCL-5), the Mini-IPIP, a 20-item short form of the International Personality Item Pool measure of the Big Five personality traits, the Ruminative Responses Scale (RRS) short form, and the Patient Global Impression of Improvement (PGI-I) – a one item self-report assessment of improvement of urinary symptoms. In addition, at both follow-up assessments, participants will be asked whether they have received any treatment outside of the study for their urinary symptoms and/or their anxiety. Any treatment participants receive outside of the study will be tracked in this manner and included in data analyses.

Table 2. Timing of Assessments

Measure	Estimated Completion Time	Baseline	Session 6	Session 12	3 Month Post-Treatment Follow-up	6 Month Post-Treatment Follow-up
Medical history and physical exam	0 (part of regular medical visit and extracted from EMR)	X				
Demographic questionnaire	1 min	X				
Single Item Literacy Screener (SILS)	< 1 min	X				
Brief Medication Questionnaire (BMQ) 	3-5 min	X			X	X
Primary outcome 1: PROMIS Anxiety subscale of profile (4 of 29 items below)	See below for entire profile	X	X	X	X	X
Primary outcome 2: Urinary symptoms using the Urinary Distress Inventory (UDI-6) of the Pelvic Floor Distress Inventory (PFDI)	1-3 min	X	X	X	X	X
Secondary outcomes:						
• PROMIS Profile (29 items)	5-10 min	X	X	X	X	X
• PGI-I	< 1 min			X	X	X

Secondary correlates:						
• PTSD Checklist for DSM-5 with Life Events Checklist (PCL-5)	10 min	X				
• Mini-IPIP	3-5 min	X				
• Ruminative Response Scale (RRS)	1-3 min	X				
• Follow-up treatment questions	1-3 min				X	X

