#### **4.0 Sample Size:**

This study will include up to 40 participants. UP-CBT has been shown to have quite large effects (Cohen's  $d$  values of 1.7 or greater). For this study, we have chosen a slightly more conservative estimate for Cohen's  $d$  of 1.5, which represents 1.5 standard deviations between the treatment effect of UP-CBT versus the control group. Based on a power analysis, we would require 16 women per group, in the data analyzed, to detect a treatment effect with  $> 98\%$  power with a Type I error rate of  $\alpha = .05$ , two-tailed. Study withdrawal is estimated at roughly 20%, leaving an estimated final sample of 32 participants for data analysis (see CONSORT diagram below).

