#### 8.4 Therapy

Participants will be scheduled to come to an individual treatment session once per week for 12 weeks, at a convenient time for them, on the Northwestern Campus. This arrangement allows for a one-stop experience for the patient, maximizing their convenience. As described above, participants will be randomized to one of two therapy conditions: UP-CBT or supportive therapy. All sessions, in both conditions, will be 45 minutes in duration. If a participant happens to miss or cancel a session they will be rescheduled.

Unified-Protocol Cognitive Behavior Therapy (UP-CBT) is a form of therapy that draws upon various forms of cognitive-behavior therapy to “unify” the most important tools into one protocol. Cognitive-behavior therapy has been a leading treatment for depression and anxiety for decades, but historically has focused on specific disorders (e.g., major depression, social anxiety disorder, panic disorder). UP-CBT includes a variety of general-purpose techniques to help people cope more skillfully with emotionally stressful situations. This includes dealing with emotional situations by reappraising negative thoughts (e.g., “If I get nervous at work, the stress I feel will be temporary and won’t kill me” rather than “I can’t deal with my life”). UP-CBT focuses on dealing with stress in general, but its techniques are readily adaptable to dealing with urinary symptoms. For example, a woman might have catastrophic thinking about urine leakage (“What if someone notices that I’ve leaked?”). These catastrophic thoughts can result in strong fear responses, as well as potentially problematic behaviors (e.g., avoidance of social situations or even skipping work). In general, UP-CBT teaches people to track emotions, thoughts, and behavior in an effort to identify maladaptive patterns. In addition, participants learn to restructure their thoughts, and to more confidently confront situations that they find challenging. Towards the end of treatment, patients learn to prevent relapses through practice of therapy skills. Participants in the UP-CBT group will be asked to complete homework outside of the therapy session, to practice therapy skills. Homework will be completed in their therapy workbook, and they will be instructed to bring their workbook to each session. After completing the 12 sessions, participants will be able to keep their workbook.

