### 8.5 Analysis Plan

**Primary analyses.** We will create hierarchical linear models (HLM) to test the primary hypotheses of the study. One model will determine the effect of type of therapy on anxiety. A separate model will determine the effect of type of therapy on urinary symptoms. The dependent variables for these models will be the UDI-6 subscale of the PFDI-20 and anxiety as measured by the anxiety subscale of the PROMIS Profile-29. The structure of the HLM model is shown below. Note that these models create a response profile for each person across all time points as described in the protocol.

#### Level 1

$$Y = P_0 + P_1(T_2) + P_2(T_3) + P_3(T_4) + P_4(T_5) + E$$

#### Level 2

$$P_0 = B_{00} + B_{01}(\text{Condition})$$

$$P_1 = B_{10} + B_{11}(\text{Condition}) + R_1$$

$$P_2 = B_{20} + B_{21}(\text{Condition}) + R_2$$

$$P_3 = B_{30} + B_{31}(\text{Condition}) + R_3$$

$$P_4 = B_{40} + B_{41}(\text{Condition}) + R_4$$

The dummy variables P1-P4 are dummy codes for the five time points. These will allow us to determine the degree of change from baseline. Each of the "P" coefficients is influenced by Level-2 variables. T2 - T5 are dummy variables of the time differences from baseline. E, R1-R4 represent error terms in the model. Condition will be dummy coded (UP-CBT = 1, Supportive Therapy = 0).

**Testing Key endpoints.** We have two primary endpoints and therefore we will have two models. For both anxiety (PROMIS T score) and urinary symptoms (UDI-6), the full model (see above) will be compared to a reduced model with all of the terms involving condition removed (i.e., B01, B11, B21, B31, and B41). If this comparison is significant ( $p < .05$ ), then we will test individual parameters at a Type I error rate of alpha = .05 (two-tailed). Note, these tests will only be carried out if the full-reduced model comparison is

significant. The key prediction for anxiety is that parameters B21, B31, and B41 (representing the effect of UP-CBT at post-treatment and beyond) will be significant and negative (representing fewer symptoms). The key prediction for urinary symptoms is that parameters B21, B31, and B41 (representing the effect of UP-CBT at post-treatment and beyond) will be significant and negative (representing fewer symptoms).

**Missing data.** All participants with baseline data will be included in the modeling using an intent-to-treat approach. The HLM approach described above can accommodate cases with missing follow-up data.

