## **15.0 Risks to Participants:**

Participating in this study involves minimal risks. It is possible that participants may feel some shame, emotional discomfort, distress, boredom/fatigue when completing the assessments of urinary symptoms, depression, and anxiety, or when participating in therapy. If we find that participants in the study are at risk for harming themselves or others, we will follow the protocol to connect the participant with crisis services, and document the situation accordingly. We will inform participants that their participation in this study may result in a loss of privacy. This includes data from questionnaires entered into a computerized database, questionnaires completed online, as well as written therapy notes. Several steps will be taken to protect confidentiality and minimize the above risks.

If a participant withdraws from any part of the study (e.g., does not complete one of the surveys), they are welcome to participate in other aspects of the study. If a participant chooses to withdraw from the study, data that has been collected during their participation will be analyzed unless the participant specifies otherwise.

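### Mid- and post-treatment outcomes are timed only by session count, so a woman who stops therapy has no scheduled post-treatment assessment and B21 rests on an unstated missing-at-random assumption

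*Combined protocol and SAP*

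**What the plan says.** Section 8.3 sets the two on-treatment assessments at "mid-treatment (after 6 sessions), posttreatment (after 12 sessions", completed on a tablet or on paper. The columns of Table 2 after baseline follow the same scheme: "Session 6 Session 12 3 Month Post-Treatment Follow-up 6 Month Post-Treatment Follow-up". For the last two, "Both follow-up assessments will be carried out online with a link sent via email".

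Section 8.4 schedules therapy "once per week for 12 weeks" and adds: "If a participant happens to miss or cancel a session they will be rescheduled". No latest date is attached to session 6 or session 12.

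Section 8.5 states the analysis aim: "All participants with baseline data will be included in the modeling using an intent-to-treat approach". It adds that the model can handle missing follow-up data, but names no missingness assumption and no sensitivity analysis. The key predictions for both primary outcomes concern B21 (post-treatment), B31 (3 months) and B41 (6 months).

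Section 15.0 says of women who withdraw from one part that "they are welcome to participate in other aspects of the study". Section 4.0 plans for loss: "Study withdrawal is estimated at roughly 20" per cent, taking 40 enrolled to 32 analysed.

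**The concern.** An intent-to-treat contrast needs the outcome of every randomised woman at a comparable time, whatever therapy she received. Here the event that prompts the post-treatment questionnaire is the twelfth session itself. A woman who stops at session 4 or session 9 never reaches it, so her post-treatment outcome is missing because she stopped. Section 15.0 allows her to carry on with other parts of the study, but it gives permission only. It sets no trigger and no date, and its example is a skipped survey, not stopped therapy.

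At stake is the meaning of B21 for both primary outcomes. Two of the three mediation paths in section 8.5 also use the mid- or post-treatment assessment. Rescheduling adds a smaller problem: post-treatment can fall at different calendar times for different women, with no limit.

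**Working it through.** **1. What each woman contributes if the text is followed.**

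- Stops before session 6: no trigger for T2 (mid-treatment) or T3 (post-treatment). T4 and T5 can be emailed, but their start date is undefined.
- Stops after session 6 and before session 12: T2 is defined and T3 has no trigger. T4 and T5 are as above.
- Completes session 12: all four are defined.

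Observed T3 data therefore come only from women with 12 sessions. B31 and B41 are touched only through the unclear anchor date.

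**2. What the model does with the gap.** Everyone with baseline data enters the model. Under missing at random, a woman without T3 is in effect given the course of similar women who continued, using whatever else she supplied (T2, or T4 and T5 if collected). That moves B21 toward the effect had therapy been continued. For a woman with baseline data only, the printed equations help little: the Level-2 equation for P0 has no random term. If Level-1 errors are independent, her baseline score informs the baseline mean but not the T3 mean.

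**3. The plan's own figures.** With 16 per group, d = 1.5 and two-sided alpha 0.05, the noncentrality is 1.5 / √(1/16 + 1/16) = 4.24 on 30 degrees of freedom. Power is 98.4% (98.9% by the normal approximation), and 40 × 0.8 = 32. The stated power above 98% and the sample size reproduce. The timing gap does not make them wrong; it bears on which effect is estimated.

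**4. Illustration of the difference in effect.** Assume 20% of women stop therapy, none of them has T3 data, and 1.5 SD is the effect in completers. Let f be the share of benefit that stoppers keep. The all-randomised effect is 0.8 × 1.5 + 0.2 × 1.5 × f.

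- f = 0: 1.20, and 1.5 / 1.20 = 1.25.
- f = 0.5: 1.35, and 1.5 / 1.35 = 1.11.
- f = 1: 1.50, no difference.

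**5. Bias when there is no true effect.** This was simulated with 20 women per arm, a baseline-adjusted comparison of those observed (simpler than the plan's model), baseline-outcome correlation 0.5, and stopping correlated 0.6 with a worse outcome. All of these are assumptions.

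- 20% stopping in each arm: bias about 0, rejection 5.3%.
- 30% in UP-CBT and 10% in supportive therapy: bias -0.14 SD, rejection 7.3%.
- The same split with correlation 0.3: bias -0.08 SD, rejection 5.0%.

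Negative values favour UP-CBT. By symmetry, swapping the stopping rates between arms reverses the sign.

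**6. Power if every woman is assessed.** With 20 per arm (equal allocation assumed), 20% stopping and f = 0, the effect is 1.20 and power is 95.9% with the SD held at 1. Letting the UP-CBT arm be a mixture gives an SD there of √(1 + 0.2 × 0.8 × 1.5²) = 1.17, a pooled SD of 1.09, d = 1.10 and power 92.6%.

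**The case against.** Timing by session is a reasonable choice in a pilot: it fixes the amount of therapy received at mid- and post-treatment, and calendar timing would catch some women before they finish. The plan does not drop women who stop. All with baseline data are modelled, those who stop after session 6 supply T2, and the follow-ups need no attendance. The weekly 12-session schedule also suggests a natural end date from which follow-up could be counted. Figure 1, the participant flow, could not be checked; if it sets an assessment for women who discontinue, the point narrows.

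Most of this stands, and it rules out several stronger readings that a reader might infer.

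- That the trial becomes a completer analysis. Not by rule: B31 and B41 have their own data, and T2 informs the model.
- That the bias favours UP-CBT. Nothing in the documents establishes that. It depends on who stops in which arm and how they fare, and step 5 gives about zero bias with equal stopping and no true effect.
- That the plan's 20% implies a 25% overstatement. Section 4.0 gives withdrawal from the study, not stopping therapy while still reachable, and it does not call 1.5 a completer effect.
- That homework makes assessments drift more in the UP-CBT arm. Session number, length and rescheduling are the same in both arms, and nothing links homework to missed sessions.

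What the objection does not supply is a T3 assessment for a woman who stops, or a date from which her follow-ups run.

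**Conclusion.** The point holds in a limited form. The trigger in section 8.3 and Table 2 ties a missing post-treatment outcome to stopping therapy. B21 therefore rests on women with 12 sessions plus an unstated missing-at-random assumption, which does not match the intent-to-treat aim in section 8.5. B31 and B41 are affected only through an anchor date that is undefined for women who stop. The stated power and sample size are unaffected.

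The size and direction of any bias are unknown. The figures 1.20 and 1.35 against 1.5 illustrate the gap under assumed stopping and retained benefit; they do not predict it. The documents give no rate for women who stop therapy but stay in the study, the only group a change in timing can help. The change is still worth making, because outcomes not collected cannot be recovered in the analysis.

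**What to change.** In section 8.3 and Table 2:

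- Take T2 and T3 at sessions 6 and 12 if these are reached within a stated window from randomisation. Otherwise email the REDCap link at a fixed fallback week.
- Date the 3- and 6-month follow-ups from the scheduled end of the 12-week period for every randomised woman.
- State that women who stop therapy but do not withdraw from the study are sent all remaining questionnaires.
- Record the number of sessions attended.

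In section 8.5, name the missing-data assumption and add a sensitivity analysis for outcomes missing after stopping.

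The cost is protocol wording and a dated email. Emailed links are already planned for the follow-ups, although a date trigger is not described. There are three downsides. Some women will be assessed before finishing rescheduled sessions. Women who stop will answer by email while others use a tablet or paper, so mode is partly mixed with treatment status. For a woman whose sessions run late, the follow-ups fall closer to her last session than their labels suggest. Women who leave the study altogether remain unobserved.

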#### 8.4 Therapy

Participants will be scheduled to come to an individual treatment session once per week for 12 weeks, at a convenient time for them, on the Northwestern Campus. This arrangement allows for a one-stop experience for the patient, maximizing their convenience. As described above, participants will be randomized to one of two therapy conditions: UP-CBT or supportive therapy. All sessions, in both conditions, will be 45 minutes in duration. If a participant happens to miss or cancel a session they will be rescheduled.

Unified-Protocol Cognitive Behavior Therapy (UP-CBT) is a form of therapy that draws upon various forms of cognitive-behavior therapy to “unify” the most important tools into one protocol. Cognitive-behavior therapy has been a leading treatment for depression and anxiety for decades, but historically has focused on specific disorders (e.g., major depression, social anxiety disorder, panic disorder). UP-CBT includes a variety of general-purpose techniques to help people cope more skillfully with emotionally stressful situations. This includes dealing with emotional situations by reappraising negative thoughts (e.g., “If I get nervous at work, the stress I feel will be temporary and won’t kill me” rather than “I can’t deal with my life”). UP-CBT focuses on dealing with stress in general, but its techniques are readily adaptable to dealing with urinary symptoms. For example, a woman might have catastrophic thinking about urine leakage (“What if someone notices that I’ve leaked?”). These catastrophic thoughts can result in strong fear responses, as well as potentially problematic behaviors (e.g., avoidance of social situations or even skipping work). In general, UP-CBT teaches people to track emotions, thoughts, and behavior in an effort to identify maladaptive patterns. In addition, participants learn to restructure their thoughts, and to more confidently confront situations that they find challenging. Towards the end of treatment, patients learn to prevent relapses through practice of therapy skills. Participants in the UP-CBT group will be asked to complete homework outside of the therapy session, to practice therapy skills. Homework will be completed in their therapy workbook, and they will be instructed to bring their workbook to each session. After completing the 12 sessions, participants will be able to keep their workbook.

Supportive therapy is a non-active form of psychotherapy that has been widely used as a control condition in therapy studies. Many of the elements of supportive therapy may be beneficial to some participants, just as pill placebos benefit some participants in drug trials. As such, it is an excellent control condition because it is not merely “sham

therapy". Supportive therapy is widely-used in clinical community settings. In this condition, no cognitive-behavioral exercises will be used. Supportive Therapy allows for careful control over the number of therapy sessions and time per session. Thus, it is ideal for being able to match to UP-CBT. The protocol for supportive therapy will include 1) education about urinary symptoms, anxiety, and depression, 2) discussion of patient goals, 3) sharing of concerns in a nonjudgmental environment, 4) discussion of the possible connections between urinary symptoms and emotional distress, and 5) reflective listening. Participants in supportive therapy will *not* be given homework.

#### 8.4.1 Therapy Progress Notes

Therapists will complete brief progress for each participant after each session in both therapy conditions. Progress notes will be used only for research purposes, and will not be added to the medical record. Progress notes will be available to participants upon their request after study completion (including completion of follow-up assessments).

### 8.5 Analysis Plan

**Primary analyses.** We will create hierarchical linear models (HLM) to test the primary hypotheses of the study. One model will determine the effect of type of therapy on anxiety. A separate model will determine the effect of type of therapy on urinary symptoms. The dependent variables for these models will be the UDI-6 subscale of the PFDI-20 and anxiety as measured by the anxiety subscale of the PROMIS Profile-29. The structure of the HLM model is shown below. Note that these models create a response profile for each person across all time points as described in the protocol.

#### Level 1

$$Y = P_0 + P_1(T_2) + P_2(T_3) + P_3(T_4) + P_4(T_5) + E$$

#### Level 2

$$P_0 = B_{00} + B_{01}(\text{Condition})$$

$$P_1 = B_{10} + B_{11}(\text{Condition}) + R_1$$

$$P_2 = B_{20} + B_{21}(\text{Condition}) + R_2$$

$$P_3 = B_{30} + B_{31}(\text{Condition}) + R_3$$

$$P_4 = B_{40} + B_{41}(\text{Condition}) + R_4$$

The dummy variables P1-P4 are dummy codes for the five time points. These will allow us to determine the degree of change from baseline. Each of the "P" coefficients is influenced by Level-2 variables. T2 - T5 are dummy variables of the time differences from baseline. E, R1-R4 represent error terms in the model. Condition will be dummy coded (UP-CBT = 1, Supportive Therapy = 0).

**Testing Key endpoints.** We have two primary endpoints and therefore we will have two models. For both anxiety (PROMIS T score) and urinary symptoms (UDI-6), the full model (see above) will be compared to a reduced model with all of the terms involving condition removed (i.e., B01, B11, B21, B31, and B41). If this comparison is significant ( $p < .05$ ), then we will test individual parameters at a Type I error rate of alpha = .05 (two-tailed). Note, these tests will only be carried out if the full-reduced model comparison is

significant. The key prediction for anxiety is that parameters B21, B31, and B41 (representing the effect of UP-CBT at post-treatment and beyond) will be significant and negative (representing fewer symptoms). The key prediction for urinary symptoms is that parameters B21, B31, and B41 (representing the effect of UP-CBT at post-treatment and beyond) will be significant and negative (representing fewer symptoms).

**Missing data.** All participants with baseline data will be included in the modeling using an intent-to-treat approach. The HLM approach described above can accommodate cases with missing follow-up data.

**Mediation analysis.** We will also carry out mediation analysis in Mplus using bias-correct bootstrapped 95% confidence intervals. We will hypothesize that these confidence intervals will not contain zero for the following mediated effects:

Condition → Mid-treatment anxiety → Post-treatment urinary symptoms

Condition → Post-treatment anxiety → 3-month urinary symptoms

Condition → 3-month anxiety → 6-month urinary symptoms

In addition to testing statistical significance, our hypothesis is directional. Condition (i.e., receiving UP-CBT) should lead to lower anxiety, in turn leading to lower urinary symptoms.

**Exploratory analyses.** Although our primary focus is anxiety and urinary symptoms, we will conduct HLM analyses on each scale of the PROMIS Profile (depression, fatigue, sleep, pain interference, pain, social function) and other subscales of the PFDI (total score, colorectal symptoms, pelvic organ prolapse symptoms). These analyses will be clearly marked as exploratory in all write-ups. We will also create a prediction model of treatment response (i.e., trajectory of symptoms) based on baseline characteristics. These will also be clearly marked as exploratory in all study write-ups.

Table 3. Project Timeline

	Months 1-2	Months 3-4	Months 5-6	Months 7-8	Months 9-10	Months 11-12	Months 13-14
IRB Approval							
Staff Training							
Recruitment							
Pilot RCT Study							
Follow-up Assessments							
Data Analysis							
Manuscript write-up							

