### **1.3 Hypotheses**

1. We hypothesize that UP-CBT will reduce anxiety, and urinary symptoms in women suffering from lower urinary tract symptoms, at post treatment and follow-up.
2. UP-CBT will be compared to a control condition, supportive therapy. Supportive therapy, although often used in clinical settings (e.g., in support groups), is not expected to reduce anxiety, or urinary symptoms on average. Thus, we expect that the benefits of UP-CBT will be greater than benefits of the control therapy, supportive listening.

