#### **8.0 Procedures Involved:**

##### **8.1 Randomization and Study Design**

This is a pilot study to test pre-post changes associated with UP-CBT, urinary symptoms, and emotional distress. Women eligible for the study will be randomized to treatment based on a predetermined list created using the `blockrand` package of R. Randomization will occur by blocks, with varying block sizes, in accord with recommended methods for RCTs. The randomization key will be linked to a unique study ID number, as well as to a treatment condition (UP-CBT or Supportive Therapy).

[figure not shown]

Figure 1. Study Design CONSORT Flow Diagram

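### The primary model has no person-level term on the intercept, so as printed it treats each woman's baseline as uncorrelated with her later scores and misstates the standard errors of B21, B31 and B41

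*Combined protocol and SAP*

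**What the plan says.** Section 8.5 writes the model out in equations. Level 1 has an intercept P0, four visit dummies with coefficients P1 to P4, and an error E. At Level 2, P1 to P4 each carry a condition effect and a random term (R1 to R4). P0 is B00 + B01 × Condition, with no random term. The prose agrees with the equations: "E, R1-R4 represent error terms in the model". No covariance structure is given for E or for R1 to R4, and robust standard errors are not mentioned.

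The same model serves three purposes, for both UDI-6 and PROMIS Anxiety:

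- **Gate.** "the full model (see above) will be compared to a reduced model with all of the terms involving condition removed". Five terms are dropped (B01, B11, B21, B31, B41). No test statistic is named.
- **Individual tests.** B21, B31 and B41 are each tested at two-sided .05, and "these tests will only be carried out if the full-reduced model comparison is" significant.
- **Missing data.** "The HLM approach described above can accommodate cases with missing follow-up data". Section 4.0 expects losses: "Study withdrawal is estimated at roughly 20"%.

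Section 1.3 claims benefit "in women suffering from lower urinary tract symptoms, at post treatment and follow-up", so B31 and B41 carry part of the main claim alongside B21.

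**The concern.** The same woman answers the same items at baseline and at four later visits, so her baseline should correlate with her later scores. A random intercept, or an error covariance that links all five visits, normally carries that correlation. The printed model has neither. R1 to R4 let the four later visits correlate with one another, but nothing ties them to baseline.

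Three things are at stake. The standard errors of the key change-from-baseline parameters omit the covariance term. The gate is computed from the same covariance. And a woman's baseline score cannot inform her missing later scores, which removes much of the reason for keeping everyone with baseline data in the model.

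**Working it through.** **The plan's own figure.** Section 4.0 gives 16 per group analysed, d = 1.5, two-sided .05 and power above 98%. As a two-group t-test the noncentrality is 1.5 × √(16/2) = 4.24 on 30 df, and power is 98.4%. Enrolment is 32/(1 − 0.20) = 40. Both reproduce. This is not a power calculation for the hierarchical model, and the point made here does not disturb it.

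**Algebra.** Take E independent across visits, with variance s², and independent of R. Then:

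- baseline = fixed part + E₁, with variance s²
- visit t = fixed part + R + E_t, with variance Var(R) + s²
- hence Cov(baseline, visit t) = 0, and Var(visit t) ≥ Var(baseline)

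With n per arm, the fitted variance of B21 is (2/n)[V(base) + V(t)]. The true one is (2/n)[V(base) + V(t) − 2Cov].

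**Maximum-likelihood fit of this structure.** s² becomes the mean of the baseline variance and those eigenvalues of the follow-up covariance block that lie below s². Larger eigenvalues are kept.

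**Worked case** (assumed: unit variances, all correlations .5). The follow-up eigenvalues are 2.5, .5, .5, .5.

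- s² = (1 + 3 × .5)/4 = 0.625
- fitted follow-up variance = (2.5 + 3 × 0.625)/4 = 1.094
- fitted Var(change) = 0.625 + 1.094 = 1.719; true = 2 − 2 × .5 = 1
- SE ratio = √1.719 = 1.31; level = 2P(Z > 1.96 × 1.31) = .010

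**Large-sample results, individual tests without the gate.** All patterns are assumptions. Decay is AR(1) by visit, or in calendar time with weeks 0/6/12/25/38 and rho per 6 weeks.

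| Assumed pattern | Fitted SE / true SE | Level |
|---|---|---|
| Equal variances, constant .3/.5/.7 | 1.14/1.31/1.64 | .025/.010/.001 |
| Equal variances, either decay, .3 to .7 | 0.94 to 1.32 | .066 to .010 |
| Follow-up SD 0.7, constant .1/.3/.5/.7 | 0.93/1.02/1.16/1.41 | .067/.045/.023/.006 |
| Follow-up SD 0.7, decay by visit .3 | B21 0.93; B41 0.88 | .070; .086 |
| Follow-up SD 0.7, calendar decay .5 | B41 0.86 | .091 |

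**The plan's full sequence, simulated.** There were 20,000 complete trials per pattern, 16 per arm, rho .1 to .7. The gate is assumed to be a 5-df ML likelihood ratio at .05, and the individual tests REML t on 30 df.

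- *No effect at any visit:* gated B41 rejects at most .027 (equal variances) or .044 (follow-up SD 0.7).
- *Fading effect* (assumed 0.75 SD at session 6, 1.5 SD at session 12, none afterwards): the gate passes in .90 to 1.00 of trials. B41 false positives are .001 to .062 (equal variances) or .006 to .085 (follow-up SD 0.7). With the corrected model they are .050 to .053.
- *Gate itself under no effect:* .074 to .103 (equal variances) or .077 to .117 (follow-up SD 0.7).
- *Gated power of B21 at d = 1.5* (d/2 at session 6, then d at every later visit), equal variances, rho .3/.5/.7: constant correlation .896/.931/.970 as printed against .932/.984/>.99 corrected; decay by visit .863/.889/.920 against .855/.908/.969.

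**Dropout.** Suppose 20% of 40 women leave before session 6 and the odds of leaving double per baseline SD in one arm only. The mean baseline of those retained in that arm shifts by −0.129 SD. Expected bias in B21 is rho × shift: −0.039/−0.065/−0.090 SD for rho .3/.5/.7. Simulation gives −0.042/−0.068/−0.094 as printed and −0.003/−0.003/−0.002 with an unstructured covariance. If the link is the same in both arms, B21 has no bias.

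**The case against.** The strongest reply is that this is a gap in specification. The plan never says that E is independent, and it speaks of a response profile for each person, so within-person modelling was intended. That is fair as to intent, but the phrase fixes no covariance. The equations are offered as the structure, and equations and prose agree on the omission. An analyst who simply adds R0 to unstructured R1 to R4 plus E has 16 parameters for 15 variances and covariances, so the repair is not self-evident.

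Several limits stand:

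- Direction is unknown, and in some patterns the errors nearly cancel (ratio 1.02 above). With follow-up SD 1.3 times baseline the lowest ratio found was 0.989 (level .053), so the tests are then mostly conservative. Nothing in the documents says variance will shrink.
- With no effect at any visit, the gate holds B41 below .05. The excess needs an effect that works and then wears off, and at equal variances it reaches only .062.
- At d = 1.5 the power cost for B21 is small under decay (5 points lost to 1 gained). For B41 under decay the printed model can be up to 4 points higher, mainly where its test is anti-conservative.
- The dropout bias needs a link that differs between arms, and it is small against 1.5 SD.
- The fitted R covariance is singular in nearly all equal-variance simulated trials. The figures assume that fit is accepted, and software may instead flag it.
- The unnamed gate statistic, and the small-sample inflation of a likelihood-ratio gate, are separate from the missing intercept term.
- Kenward-Roger is one defensible choice among several.

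The trial also describes itself modestly: "This is a pilot study to test pre-post changes associated with UP-CBT". None of this makes the printed covariance right.

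**Conclusion.** The concern holds. Unless E may correlate across visits, which the plan does not say, the printed model sets the covariance between baseline and every later visit to zero, and the standard errors of B21, B31 and B41 are correct only by coincidence. Over the patterns tabulated, the ungated level of a nominal .05 test runs from .001 to .091. It is conservative under equal variances and constant correlation. It can be anti-conservative, chiefly for B41, under decaying correlation or reduced follow-up variance. These sizes rest on assumed correlations and variances, because the documents give none.

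Complete-data point estimates and the sample-size figure stand. This should be fixed before analysis; in a pilot the consequence is modest.

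**What to change.** Keep the fixed effects, hypotheses and sample size. Change the covariance and the tests in 8.5 as follows:

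- **Covariance.** Replace R1 to R4 and E with one unstructured 5×5 within-woman covariance and no random effects. Fit by REML with Kenward-Roger degrees of freedom for B21, B31 and B41.
- **Gate.** From the same fit, use a joint 5-df Kenward-Roger F test of B01, B11, B21, B31 and B41. REML likelihoods cannot be compared across different fixed effects. The unstructured ML likelihood ratio rejects too often at n = 32: P(F(5,26) > (26/5)(exp(11.07/32) − 1)) = .091. The F test gives .050.
- **Fallback if the fit does not converge, in order.** Heterogeneous Toeplitz (SE ratio 0.98 to 1.10 across the patterns tried), then random intercept plus AR(1) residuals with visit-specific variances (0.97 to 1.08). With one common residual variance the second falls to 0.87 to 0.98 when follow-up SD is 0.7 of baseline.
- **Avoid.** Adding R0 to the printed terms is not identified. A random intercept alone gives a B41 SE of 0.92/0.86/0.80 of the true SE under decay by visit at rho .3/.5/.7 and equal variances.

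The cost is SAP wording and a few lines of code, with no extra data or patients. The downside is 15 rather than 11 covariance parameters in a small sample, and up to 4 points less B41 power at d = 1.5 if correlation decays. In 16,000 simulated null fits with 40 women and 20% dropout, none failed to converge. The gate rejected .048 to .054 and the individual tests .046 to .057.
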